5.4 Visit 4 – Stage II: Second Radiofrequency Treatment (6 weeks later)

The study physician will perform a brief history and examination to make sure the patient tolerated the first treatment well and that the patient's tissues are fully healed with no visible ulceration or granulation. If there is a complication such as abscess and ulceration, the second treatment will be delayed until patient's tissues are fully healed. The patient will be given oral antibiotics and will then undergo a second treatment as outlined above. Treatment will be done in the same region and location since there is no concern about RFA lesion overlap once the tissues have healed. The patient will be prescribed pain medication if needed, along with a short course of oral antibiotics and steroids as outlined above.

After completion of both RFA procedures, the research team will monitor the patient for up to 3 hours post-procedure. Patients must demonstrate adequate pain control, breathing, swallowing and speech prior to discharge. The patient's vitals will be taken prior to the patient being released from the clinic. The research team will ask the patient to walk around the clinic for five minutes to assess the patient's post-operative status. The patient will be provided prescriptions for an antibiotic (amoxicillin or clindamycin), an oral steroid (7-day methylprednisolone taper pack), and an oral pain medication to take if needed (Acetaminophen/Hydrocodone). In addition, the patients will be asked to have a soft diet for at least 2 days after the treatment. The patient will then repeat the questionnaires specified above. Patients will be asked in advance to have their bed partner to drive them home. The research team will escort the patient and the bed partner out to the car as outlined above.

The patients will repeat the pain, speech, and swallowing VAS scales at 1, 3, and 7 days post RFA treatment via telephone in order to document persistent ongoing pain, and post-treatment discomfort. The amount of narcotic pain medication used in the first 7 days following the procedure will be recorded using pill count.

Medical examinations and medical actions needed due to development of side effects and/or complications will be the same as described in Section 5.3 above.

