1.5 Safety of RF ablation of the soft palate and base of tongue

Radiofrequency ablation of the soft palate and base of tongue is considered as a minimally invasive therapy with much less side effects and complications in comparison to other surgical therapies for OSAS^{39, 40}.

Potential specific complications of radiofrequency ablation include bleeding, infection, ulceration, palatal fistula, tongue weakness, and taste disturbance alongside globus sensation. Long-term complications are unusual but globus sensation may persist in up to 10 % of patients. Most patients recover quickly however and report improvements in snoring although a recent systematic review indicated that further long-term studies are required⁴¹⁻⁴³.

In a retrospective study, 130 patients underwent one to three sessions of RFA of soft palate (6 lesions) and base of tongue (6 lesions) with either Somnus (Gyros-ENT), or the CelonProSleep *plus* (Caroll et al.³², with █ the PI in this study). The most common complication of upper airway RFA was mucosal ulceration (11%; mild side effect⁴⁵), which healed with saline gargles within 10 days to 2 weeks. Ten patients (8%) had significant palatal or tongue edema (mild complication), which interfered with speech and/or swallowing but resolved within a few days of starting a taper dose of steroids. One patient had a temporary paresis of the lingual nerve (moderate complication), which resolved a couple of weeks after tongue base RFA. This was attributed to a pressure neuropathy from the laryngoscope because the lingual nerve was not within the field of the RFA application. No patient had a severe or prolonged dysphagia preventing oral diet immediately after the procedure. However, no information is given whether the complications caused by using the Somnus or the CelonProSleep *plus*³².

Factors that affect RFA complications may be repeated RFA treatment to the same tissue, learning curve of individual surgeons, energy delivered per lesion, temperature selection, anatomical site treated, and perioperative steroid use⁴⁵.

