5.5 Visit 5 - Stage III: Third Radiofrequency Treatment (6 weeks later)

The doctor will perform a brief history and examination to make sure the patient tolerated the second treatment well and that the patient's tissues are fully healed. If there is a complication such as abscess and ulceration, the third treatment will be delayed until patient's tissues are fully healed. The patient will be given oral antibiotics and will then undergo a third treatment as outlined above. Treatment will be done in the same region and location. The patient will be prescribed pain medication if needed, along with a short course of oral antibiotics and steroids as outlined above.

After completion of both RFA procedures, the research team will monitor the patient for up to 3 hours post-procedure. Patients must demonstrate adequate pain control, breathing, swallowing and speech prior to discharge. The patient's vitals will be taken prior to the patient being released from the clinic. The research team will ask the patient to walk around the clinic for five minutes to assess the patient's post-operative status. The patient will be provided prescriptions for an antibiotic (amoxicillin or clindamycin), an oral steroid (7-day methylprednisolone taper pack), and an oral pain medication to take if needed (Acetaminophen/Hydrocodone). In addition, the patients will be asked to have a soft diet for at least 2 days after the treatment. The patient will then repeat the questionnaires specified above. Patients will be asked in advance to have their bed partner drive them home. The research team will escort the patient and bed partner out to the car as outlined above.

The patients will repeat the pain, speech, and swallowing VAS scales at 1, 3, and 7 days post RFA treatment via telephone in order to document persistent ongoing pain, and post-treatment discomfort. The amount of narcotic pain medication used in the first 7 days following the procedure will be recorded.

Medical examinations and medical actions needed due to development of side effects and/or complications will be the same as described in Section 5.3 above.

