13.2 Investigator's Role and Responsibilities

13.2.1 Clinical Investigators

The Investigator is responsible for conducting the study in accordance with the signed agreement, the investigational plan, applicable laws, the latest version of the “Declaration of Helsinki: Recommendations Guiding Medical Doctors in Biomedical Research Involving Human Patients” and any conditions of approval imposed by the reviewing regulatory body.

The clinical investigator shall be responsible for the day to day conduct of the clinical investigation as well as for the safety and well-being of the human subjects involved in the clinical investigation.

The clinical investigator shall have the resources to conduct the clinical investigation properly and obtain from the sponsor the information which he judges essential about the device and be familiar with this information.

The clinical investigator shall ensure that adequate information is given to the subject both in oral and written form, on the nature of the clinical investigation. This information shall be easily understandable by the subject. This information shall include the aims, expected benefits for him and/or others, risks and inconveniences and an explanation of any alternative methods, and of possible consequences of any withdrawal from the clinical investigation. Subjects shall be allowed sufficient time to decide whether or not they wish to participate. The subjects shall be informed that his/her participation in the clinical investigation is completely voluntary and confidential. The subject shall be made aware that the data relating to the study may be made available to third parties while maintaining anonymity.

The investigators must obtain a written IRB approval prior to including any patients into the study.

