13.8 Protocol Deviations

An Investigator is required to conduct this study in accordance with the signed Investigator's Agreement, this investigational protocol, applicable laws and regulations, and any conditions of approval imposed by the reviewing IRB.

An Investigator shall notify the Sponsor and the reviewing IRB of any deviation from the investigational plan to protect the life or physical well-being of a subject in an emergency. Such notice shall be given as soon as possible, but no later than five working days after the emergency occurred. Except in such an emergency, prior approval by the Sponsor is required for a change in or deviations from this plan and, if these changes or deviations could affect the scientific soundness of the plan or the rights, safety or welfare of human subjects, IRB and national authority approval is also required.

All deviations from the investigational plan must be reported to Sponsor, together with the reason for the deviation. In some circumstances, the center may be required to notify the center's IRB and Sponsor will notify the national authorities and/or suspend the center's participation in this clinical trial. In these circumstances, Sponsor will perform a compliance visit to evaluate adherence to the investigational plan, compliance with applicable regulations, and any additional specific issues related to the event. Additional training on the protocol and related procedures may also be necessary. Prior to continuing involvement in this clinical trial, the results of Sponsor compliance visit and concurrence from the center's IRB and/or national authorities may also be required. At this time Sponsor will ask the Investigator to review the Investigator Agreement and applicable regulations regarding medical device clinical studies, specifically Investigator responsibilities.

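### A patient whose RFA is stopped for safety after session 1 or 2 falls outside the primary analysis as 3.1.2 is worded, and 5.4/5.5 do not say that the course may be ended

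*Combined protocol and SAP*

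**What the plan says.** **Treatment rules.** Before session 2 the physician checks that session 1 was tolerated well and that the tissues have healed. Section 5.4 then says: "If there is a complication such as abscess and ulceration, the second treatment will be delayed until" healing is complete. It continues: "The patient will be given oral antibiotics and will then undergo a second treatment as outlined above". On the site it says: "Treatment will be done in the same region and location since there is no concern about RFA lesion overlap once the tissues have healed". Section 5.5 repeats the pattern for session 3: "If there is a complication such as abscess and ulceration, the third treatment will be delayed until" healing, then "The patient will be given oral antibiotics and will then undergo a third treatment as outlined above". Neither section sets a maximum delay or a criterion for ending the course. Section 1.5 remarks: "Factors that affect RFA complications may be repeated RFA treatment to the same tissue".

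**Authority.** Section 13.2.1 makes the investigator responsible for the conduct of the study "as well as for the safety and well-being of the human subjects involved in the clinical investigation". Sections 11.0 and 13.8 allow a deviation in an emergency, with notification afterwards. Beyond that: "Except in such an emergency, prior approval by the Sponsor is required for a change in or deviations from this plan". IRB and national authority approval is added where subjects' safety or welfare could be affected. Section 13.7 admits only the patient's own request as a reason for leaving the study.

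**Analysis rules.** Section 3.1.2 restricts the primary analysis to patients with all three sessions and the 6-month assessment. The full analysis set in 8.4 requires all 8 visits, three of which are RFA visits. Section 3.1.1 counts as non-responders, among others, patients with (b) an unsuccessful treatment attempt or (c) a need for another OSA treatment. Section 8.2 mentions an intent-to-treat analysis under additional analyses.

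**The concern.** Take a willing patient who has a complication in the Severe category of 3.5 after session 1 and heals. The physician judges further ablation at the same site unwise. Sections 5.4 and 5.5 do not describe this decision, so it is unclear whether it follows the protocol or departs from it.

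The analysis consequence is the more important one. A patient who could not finish the course because of harm from the device is a treatment failure in any ordinary sense. Section 3.1.2 removes that patient from numerator and denominator alike, which raises the observed responder rate if the patient would otherwise count as a failure. Section 3.1.1 points the other way, but a non-responder label has no effect on someone outside the analysed population.

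**Working it through.** **1. Reproduce the plan's figure.** Inputs from 3.2: p0 = 0.50, p1 = 0.70, n = 43, reject if Z ≥ 1.96, with Z = (x/n − 0.5)/√(0.25/n). The smallest passing count at n = 43 is 28. The exact binomial tail is 0.0330 at p = 0.50 and 0.8081 at p = 0.70. Both match the plan.

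**2. How many patients.** The documents give no rate of stopped courses, so complication rates in 1.5 stand in for it.

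- Study device: seven studies, 199 patients, no major complication reported. One-sided 95% upper bound: 1 − 0.05^(1/199) = 1.5%; × 48 = 0.7 patients.
- Cited complication review (almost entirely other devices), per session. Only sessions 1 and 2 have a later session to cancel: 48 × 2 = 96.
  - Major only: 96 × (10/1392 + 1/1406) = 0.76.
  - Moderate or major: 96 × (38/1392 + 8/1406) = 3.2.
- Same review per patient, assuming at most one event each and adding the two sites, over all sessions.
  - Major only: 48 × (10/614 + 1/669) = 0.85.
  - Moderate or major: 48 × (38/614 + 8/669) = 3.5.

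The range is therefore about 0-1 of 48 if only major events end a course, and about 3 if moderate events also do. The review rates may be high for this trial: 1.5 gives 750 J per tongue lesion for the other devices, and 5.3 plans 80-84 J. One 30-patient series in Table 1, with another device, lists 4 severe complications (48 × 4/30 = 6.4); it is an outlier.

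**3. Effect on the rate.** 28/43 = 65.1%; 28/44 = 63.6%. One restored non-responder costs about 1.5 points.

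**4. Effect on the conclusion.** The normal-approximation lower limit is p − 1.96√(p(1−p)/n).

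| Result | Z | 97.5% lower limit | Exact one-sided p |
|---|---|---|---|
| 28/43 | 1.98 | 0.509 | 0.033 |
| 28/44 | 1.81 | 0.494 | 0.048 |

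Under the Z rule the first passes and the second fails. Under the exact test named in 8.1, both pass at one-sided 0.05 and both fail at 0.025. Smallest passing counts by n:

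| n | Z ≥ 1.96 | exact ≤ 0.05 | exact ≤ 0.025 |
|---|---|---|---|
| 42 | 28 | 27 | 28 |
| 43 | 28 | 28 | 29 |
| 44 | 29 | 28 | 29 |
| 45 | 30 | 29 | 30 |
| 46 | 30 | 30 | 31 |
| 47 | 31 | 30 | 31 |
| 48 | 31 | 31 | 32 |

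An added non-responder matters only where the cut-off rises from one row to the next and the observed count sits exactly on the lower cut-off. From 47 to 48 the Z cut-off does not move, but both exact cut-offs do. At a true rate of 70%, exactly 28 of 43 has probability 0.100.

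**The case against.** **On safety.** The strongest reply is that nothing compels treatment. The physician must make sure that the previous session was tolerated, not only that the tissue has healed, and a severe event can fail that check. Delay has no limit. A patient awaiting approval is simply not treated. The investigator carries responsibility for safety, examinations follow on days 3 and 10, and an independent committee reviews events. This largely stands. A reader might infer that the protocol obliges the investigator to re-treat a patient who has been harmed; the documents do not support that. What remains is that failing the tolerance check has no stated consequence, so the status of a stop is unclear. Section 13.7 concerns leaving the study and is not itself at fault.

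**On the analysis.** Items (b) and (c) of 3.1.1 can be read to keep the patient as a non-responder, and visits 4 and 5 might count as completed without RFA. A reader might infer that the patient certainly leaves both the primary analysis and the full analysis set; that is too strong. For the primary analysis there are two conflicting readings, with the explicit population statement in 3.1.2 on the side of exclusion. For the full analysis set, 8.4 is silent on a visit without treatment. The conflict also touches deaths and dropouts, so the repair should be general.

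**On the remedy.** Automatic non-response would override a good sleep study after two sessions. That is true, but 3.1.1 already does this for its listed circumstances, and the measured result can still be reported.

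**Conclusion.** The point holds as a minor one. Section 3.1.2, followed literally, removes patients whose course was stopped because of harm, and the error favours the device. The gap in 5.4/5.5 is missing detail about who may end a course and how that is classed; it is not an instruction to re-treat.

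The size is about 0-1 of 48 patients if only major complications end a course and about 3 if moderate ones also do, at about 1.5 points each. This rests on complication rates as a stand-in for stopped courses, on every such complication ending the course, and on every stopped patient counting as a failure.

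A reader might multiply the 10% in the working by the chance of at least one safety stop and quote an overall probability of a changed conclusion. The working does not support a single figure: that 10% belongs to the Z rule with 43 other patients, and the answer differs by test and by number analysed. Adverse events are not lost, since the safety set includes all treated patients.

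**What to change.** **Main.** Amend 3.1.2 and the full analysis set in 8.4 so that every patient who starts RFA stays in the primary denominator. Add to 3.1.1 that a course ended for safety counts as non-response. Without the change to 3.1.2 and 8.4, the addition to 3.1.1 has no effect.

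**Secondary.** State in 5.4 and 5.5 that the investigator may end RFA for safety, with example criteria set by the sponsor and investigators, and that this is neither a deviation nor a study withdrawal (clarify 13.7). Keep the patient in follow-up to a 6-month PSG timed from the last session given. Report the number of such patients under 3.5.

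**Cost.** Amendment wording only; no extra visits or patients. Each safety stop lowers the responder rate by about 1.5 points. The general denominator also brings in dropouts. If all of the planned 10% dropped out after starting RFA and 70% of the rest responded, the rate would be 0.70 × 43/48 = 62.7%. That larger cost follows from 3.1.1(d), 3.1.1(e) and 8.5, which already class these patients as failures; the sample size in 3.2 should be checked against it.

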5.5 Visit 5 - Stage III: Third Radiofrequency Treatment (6 weeks later)

The doctor will perform a brief history and examination to make sure the patient tolerated the second treatment well and that the patient's tissues are fully healed. If there is a complication such as abscess and ulceration, the third treatment will be delayed until patient's tissues are fully healed. The patient will be given oral antibiotics and will then undergo a third treatment as outlined above. Treatment will be done in the same region and location. The patient will be prescribed pain medication if needed, along with a short course of oral antibiotics and steroids as outlined above.

After completion of both RFA procedures, the research team will monitor the patient for up to 3 hours post-procedure. Patients must demonstrate adequate pain control, breathing, swallowing and speech prior to discharge. The patient's vitals will be taken prior to the patient being released from the clinic. The research team will ask the patient to walk around the clinic for five minutes to assess the patient's post-operative status. The patient will be provided prescriptions for an antibiotic (amoxicillin or clindamycin), an oral steroid (7-day methylprednisolone taper pack), and an oral pain medication to take if needed (Acetaminophen/Hydrocodone). In addition, the patients will be asked to have a soft diet for at least 2 days after the treatment. The patient will then repeat the questionnaires specified above. Patients will be asked in advance to have their bed partner drive them home. The research team will escort the patient and bed partner out to the car as outlined above.

The patients will repeat the pain, speech, and swallowing VAS scales at 1, 3, and 7 days post RFA treatment via telephone in order to document persistent ongoing pain, and post-treatment discomfort. The amount of narcotic pain medication used in the first 7 days following the procedure will be recorded.

Medical examinations and medical actions needed due to development of side effects and/or complications will be the same as described in Section 5.3 above.

5.6 Visit 6 - Follow-Up Visit (6 weeks later)

The patient will undergo complete post-treatment evaluations including sleep history and physical examination (including height, weight, and blood pressure) as done in Baseline Visit. The patient will be asked to complete questionnaires including Epworth Sleepiness Scale (ESS), Functional Outcomes of Sleep Questionnaire (FOSQ) and 10 cm VAS concerning pain, snoring (bed partner), speech, and swallowing. The study physician will inform the patient on his/her study results and medical condition and will give recommendations for ongoing management as needed.

5.7 Visit 7- Final Follow-up Visit (6-Months later after last RF treatment)

The patient will undergo complete post-treatment evaluations including sleep history and physical examination (including height, weight, and blood pressure) as done in Baseline Visit. The patient will be asked to complete questionnaires including Epworth Sleepiness Scale (ESS), Functional Outcomes of Sleep Questionnaire (FOSQ) and 10 cm VAS concerning pain, snoring (bed partner), speech, and

swallowing. In addition, each patient will undergo a second PSG sleep study not later than 30 days after the Final Study Visit. The PSG sleep study will be conducted using standard techniques in the sleep laboratory as defined in section 5.2 above.

5.8 Visit 8 – Final Study Visit (after the PSG sleep study)

Shortly after the 2nd PSG study, the study physician will inform the patient on his/her study results and medical condition and will give recommendations for ongoing management as needed.

6 DURATION

This study has a minimum of eight visits. The first visit, the Screening Visit, is planned for determining whether patient qualifies for the study. This visit will take up to 1 hour. In the second visit, the Baseline Visit, which occurs up to 2 weeks later, standard medical history, demographics and various questionnaires will be obtained from the patient. In addition, the patient will undergo a Müller's Maneuver and will be sent to the sleep lab for a PSG study (one night). This visit will last about 60 minutes.

The third visit is the first RF treatment session and will last about 1 hour. The fourth and fifth visits involve additional RF treatments and will last about one hour each. The first follow-up visit will occur 6 weeks after the third treatment visit and will last as well about 1 hour. The 7th visit, the 6-month follow-up visit, will occur 6 months later and will be no more than 1 hour. At the end of this visit the patient will be admitted to a sleep labor for undergoing the 2nd PSG study. Finally, the 8th and final Visit will last about 30 minutes. The patients may require additional visits in case of complications that are needed to be treated in the hospital or if they have a question or concern. The entire duration of the study for an individual patient is no longer than 24 weeks plus 6 months of follow-up.

